6 STUDY DESIGN

6.1 DESCRIPTION OF THE PROTOCOL

This is an open-label, non-randomized, single arm, local multi-center study conducted in 2 parts, Phase I and Phase II.

6.2 STARTING DOSE AND DOSE ESCALATION DESIGN

The rationale for selecting the starting dose and the dose escalation design are described in [Section 4.4](#). Intra patient dose escalation is not permitted.

The dose escalation decision will be made based on dose limiting toxicities (DLTs) observed during Cycle 1 of the study treatment, and deemed to be related to the investigational medicinal product (IMP) in absence of clear evidence to the contrary after validation by the Study Committee, and if not related to a disease progression. Cumulative toxicities observed upon subsequent administrations should also be considered for the dose escalation process and the dose selection decision. The Study Committee role is described in [Section 6.9](#).

The definitions of DLTs are provided in [Section 9.1.1](#).

The Phase II part is to commence after the Cohort 2 of Phase I part has completed enrollment and DLT evaluation. Patients enrolled in Phase II part will be given the recommended dose determined in Phase I part.

6.2.1 Dose Levels

- Phase I part Cohort 1: 1/2 of global maximum administrated dose defined in TED10893 (ie. 10 mg/kg QW in Cycle 1 (4 weeks) followed by 10 mg/kg Q2W in subsequent cycles)
- Phase I part Cohort 2: Global recommended dose defined in TED10893 (ie. 20 mg/kg QW in Cycle 1 (4 weeks) followed by 20 mg/kg Q2W in subsequent cycles)
- Phase II part: Recommended dose level defined in Phase I part (10 mg/kg or 20 mg/kg QW in Cycle 1 (4 weeks) followed by Q2W in subsequent cycles)

No additional or intermediate dose level is planned in this study. Refer to [Section 1.2](#) for the treatment schema.

6.2.2 Dose Escalation

In each cohort of Phase I part, at least 3 and a maximum of 6 patients will be treated and observed for DLT in Cycle 1 (4 weeks). At least 7 calendar days must pass after dosing the first patient before dosing the subsequent patients in Cohort 1. The dose escalation rule is described in [Figure 3](#) and in below:

- If none of the 3 patients experience a DLT, the Cohort 2 or Phase II part starts.

- If 1 of the 3 patients experiences a related DLT, up to 3 additional patients are treated at the same dose level.
- If 2 or more patients experience a related DLT, the maximum administrated dose (MAD) is reached.

The above plan is summarized hereafter.

Table 2 - Dose escalation decision rule

Number of patients with DLT observed at each cohort	Dose escalation decision rule
DLT in 0/3	Proceed to the next cohort or phase
DLT in 1/3	
Enroll 3 additional patients at the same dose level :
 
• If 0 out of 3 additional patients experienced DLT (ie. 1 DLT/6 patients) → proceed to the next cohort or phase• If 1 or more of 3 additional patients experienced DLT (ie. ≥2 DLTs/6 patients) → Defines MAD and dose escalation is stopped. 
(If only 3 patients were treated at Cohort 1 and ≥2 DLTs/6 patients were confirmed in Cohort 2, 3 additional patients may be treated at the Cohort 1 dose level upon recommendation from the study committee.)

DLT in ≥2/3	
Defines MAD and dose escalation is stopped.
 
(If only 3 patients were treated at Cohort 1 and ≥2 DLTs/6 patients were confirmed in Cohort 2, 3 additional patients may be treated at the Cohort 1 dose level upon recommendation from the study committee.)

DLT evaluation Period: First cycle	

6.3 MAXIMUM ADMINISTERED DOSE / MAXIMUM TOLERATED DOSE

If a DLT in Phase I part at Cycle 1 is observed in at least 2 out of a maximum of 6 treated patients ($\geq 33\%$) at a dose level, there will be no further dose escalation and this dose level will constitute the MAD. In this circumstance, the maximum tolerated dose (MTD) is defined as one level lower dose of the MAD.

Although the dose escalation process is guided by the safety evaluation during DLT observation period, cumulative or irreversible toxicities observed in subsequent administrations should also be considered for the dose escalation and dose selection decisions, upon agreement of the study committee.

In absence of MTD, the tested dose in Cohort 2 will be defined as the recommended dose of isatuximab and to be tested in the Phase II part of the study. PK, cumulative safety and efficacy data may be used to review the recommended dose level by the study committee as needed.

Dose and phase escalation algorism are illustrated in [Section 1.3](#).

6.4 RETREATMENT OF PATIENTS

The patient must have recovered to his/her baseline status or Grade ≤ 1 for any toxicities before initiating the next dose. In those cases of clear clinical benefit, a patient can continue the study treatment until disease progression, unacceptable toxicity, or patient's decision.

6.5 DOSE DELAYS/ MODIFICATIONS

In this study, Cycle 1 consists of 4 isatuximab administrations and consecutive cycles consist of 2 isatuximab administrations.

A dose delay of up to 2 weeks is permitted in order for a patient to recover to their baseline status (see [Section 6.4](#)) or to accommodate scheduling issues (eg, holidays, weather, etc.). In case of a delay greater than 2 weeks the patient will be withdrawn from the treatment as per the investigator and the Sponsor decision. Exceptions allowed by the investigator and the Sponsor should be considered only for patients with clear objective clinical benefit.

Intra-patient dose and schedule modifications are not allowed.

6.6 GUIDELINES FOR MANAGEMENT OF ADVERSE EVENTS:

6.6.1 Management of Potential Infusion Associated Reactions (IARs)

Patient(s) should routinely receive pre-medications prior to isatuximab infusion as detailed in [Section 8.3](#) to reduce the risk and severity of IARs commonly observed with monoclonal antibodies. Infusion associated reactions (NCI-CTCAE, version 4.03 term Infusion related reaction), including “allergic/hypersensitivity reactions”, or “cytokine release syndrome/acute infusion reaction”, are defined as AEs related to isatuximab with onset typically within 24 hours from the start of the infusion.

Refer to [Appendix G](#) for diagnoses [Table 12](#) and symptoms typical of an infusion associated reaction [Table 13](#).

General guidelines for the management of IARs are provided in [Table 3](#).

Table 3 - Infusion associated reactions management

NCI CTCAE v. 4.03 criteria definition	Recommendation
Mild Grade 1 Infusion interruption not indicated; intervention not indicated	Continuation of isatuximab infusion is per the judgment of the Investigator following close direct monitoring of the patient's clinical status. Isatuximab infusion may be stopped at any time if deemed necessary. (If stopped, IAR will be classified as a Grade 2 as per NCI-CTCAE)
Moderate Grade 2 Therapy or infusion interruption indicated but responds promptly to symptomatic treatment (eg, antihistamines, NSAIDs, narcotics, IV fluids); prophylactic medications indicated for <=24 hrs.)	Stop isatuximab infusion; Give additional pre-medication with diphenhydramine 25 mg IV (or equivalent) and/ or IV methylprednisolone 100 mg (or equivalent) as needed. Isatuximab may be resumed ^a only after patient recovery, with slower infusion rate and with close monitoring. (ie. infusion may be restarted at one half of the original infusion rates. If symptoms do not recur after 30 minutes, the infusion rate may be increased in 50 mg/hour increments every 30 minutes, to a maximum of 400 mg/hour). Important: Additional blood sampling during the AE is required for analysis of markers of potential TLS (uric acid, lactate dehydrogenase [LDH], BUN, creatinine, potassium, phosphate, ionized or corrected calcium).
Severe or life-threatening Grade 3 or 4 Prolonged (eg, not rapidly responsive to symptomatic medication and/or brief interruption of infusion); recurrence of symptoms following initial improvement; hospitalization indicated for clinical sequelae. Life-threatening, consequences; urgent intervention indicated.	Stop isatuximab infusion; Give additional medication with diphenhydramine 25 mg IV (or equivalent) and/ or IV methylprednisolone 100 mg (or equivalent) and/or epinephrine as needed. Definitive treatment discontinuation. Important: Additional blood sampling during the AE is required for analysis of markers of potential TLS (uric acid, lactate dehydrogenase [LDH], BUN, creatinine, potassium, phosphate, ionized or corrected calcium).

a The infusion should be completed within 16 hours from the end of infusion preparation or a new infusion should be prepared with the remaining dose to be administered the same day.

6.6.2 Management of Potential Tumor Lysis Syndrome

General guidelines for the management of the tumor lysis syndrome are provided in [Table 4](#).

Table 4 - Tumor lysis syndrome management

Symptom	Recommended Action
Laboratory Tumor Lysis Syndrome (LTLS): 
• ≥ 2 simultaneous abnormalities within 3 days prior to and up to 7 days after start of treatment• Uric acid >8 mg/dL (>475.8 μmol/L)• Potassium >6.0 mmol/L• Phosphorus >4.5 mg/dL (>1.45 mmol/L) Corrected calcium <7.0 mg/dL (<1.75 mmol/L) or ionized calcium <1.12 mg/dL (<0.3 mmol/L) ^a	Omit isatuximab until all serum chemistries have resolved Ensure normal hydration; correct laboratory abnormalities, fluid overload, electrolyte or acid-based deviations Monitor TLS complications including renal functions Refer to "serious adverse drug reaction countermeasure manual" for TLS treatment ^b . Reinstitute isatuximab treatment at full doses after resolution
Clinical TLS (CTLS): meeting criteria for LTLS in addition to one of the following complications, 
• Acute kidney injury: increase in the serum creatinine level of 0.3 mg/dL (26.5 μmol/L) or the presence of oliguria, defined as an average urine output of <0.5 mL/kg/hr for 6 hrs.• Seizures, cardiac dysrhythmia, neuromuscular irritability (tetany, paresthesias, muscle twitching, carpopedal spasm, Trousseau's sign, Chvostek's sign, laryngospasm, bronchospasm), hypotension, or heart failure probably or definitely caused by hypocalcemia• Dysrhythmia probably or definitely caused by hyperkaliemia	

a The corrected calcium level in milligrams per deciliter = measured calcium level in milligrams per deciliter + $0.8 \times (4 \text{-albumin in grams per deciliter})$

b Serious adverse drug reaction countermeasure manual for TLS: <http://www.mhlw.go.jp/topics/2006/11/dl/tp1122-1e17.pdf>
MHLW site: http://www.mhlw.go.jp/stf/seisakunitsuite/bunya/kenkou_iryou/iyakuhin/topics/tp061122-1.html

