9. Isatuximab Safety Labs: Should a isatuximab infusion associated reaction of Grade ≥ 2 occur, additional blood sampling during the AE is required for analysis of markers of potential tumor lysis syndrome (uric acid, lactate dehydrogenase [LDH], BUN, creatinine, potassium, phosphate, ionized or corrected calcium).
10. Physical Examination: Consists of examination of major body systems including neurological, digestive, extramedullary myeloma localizations, respiratory, hepatomegaly, splenomegaly, lymphadenopathy. Only clinically relevant findings will be reported in the electronic case report form (e-CRF) as AEs.
11. Vital Signs: Heart rate (HR), temperature, respiratory rate (RR), blood pressure (BP) to be taken pre-infusion, mid-infusion (when half the volume is administered), and end-infusion on days of investigational medicinal product (IMP) administration. If the infusion rate changes because of an infusion-associated reaction, vital signs should be monitored every hour and at the end of the infusion.
12. 12-Lead ECG, 2-D Echocardiogram or Multigated Acquisition (MUGA): To be performed at screening and then as clinically indicated (the same methods must be used throughout the study). LVEF need to be checked for eligibility.
13. Hematology includes: Hemoglobin, hematocrit, RBC, WBC with differential, Mean Corpuscular Volume (MCV) and platelet counts. To be done at screening, then prior to pre-medication and IMP administration on Day 1, Day 8, Day 15 and Day 22 of Cycle 1 and on Day 1 and Day 15 of every subsequent cycle, at the EoT visit and as clinically indicated. If Grade 4 neutropenia, assess ANC every 2-3 days until ANC $\geq 0.5 \times 10^9/L$ and at least weekly thereafter until ANC $\geq 1.0 \times 10^9/L$. Perform direct and indirect coombs tests prior to the first IMP administration.
14. Not required to be repeated prior to Day 1 Cycle 1 if the screening labs were performed within 3 days prior to first IMP administration.

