**Table 8 - Biochemistry parameters**

LBTEST	LBSTRESU	LBGNNRLO - LBGNNRHI
Albumin	g/L	35 - 55
Blood Urea Nitrogen (BUN)	mmol/L	3,6 – 7,1
Corectected calcium	mmol/L	2,2 - 2,6
Chloride	mmol/L	80 - 115
Glucose	mmol/L	3,9 - 7
Bicarbonate (HCO3)	mmol/L	22 – 29
Potassium	mmol/L	3,5 – 5
Magnesium	mmol/L	0,8 - 1,2
Sodium	mmol/L	136 – 145
Phosphate	mmol/L	1 - 1,4
Protein	g/L	55 – 80
Urea	mmol/L	3,6 - 7,1

ted14095-p2-16-1-9-sap

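### Protocol Table 4 pairs a corrected-calcium limit for laboratory TLS with a far lower ionized-calcium limit, so an ionized-only sample would not flag hypocalcemia that the corrected limit flags

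*Protocol*

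**What the plan says.** Table 4 of the protocol (Section 6.6.2) defines laboratory TLS as at least two "simultaneous abnormalities within 3 days prior to and up to 7 days after start of treatment". Uric acid, potassium and phosphorus each have one limit. Calcium has two, joined by *or*: "Corrected calcium <7.0 mg/dL (<1.75 mmol/L) or ionized calcium <1.12 mg/dL (<0.3 mmol/L". Footnote a defines the corrected value as total calcium adjusted for albumin: "The corrected calcium level in milligrams per deciliter = measured calcium level in milligrams per deciliter" plus 0.8 × (4 − albumin in g/dL). When laboratory TLS is met, the recommended action is "Omit isatuximab until all serum chemistries have resolved".

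A TLS blood sample is required when a Grade 2 or higher infusion reaction occurs. Its marker list ends "potassium, phosphate, ionized or corrected calcium" in Section 1.6, footnote 9. The same choice of calcium measure appears in the Grade 2 and the Grade 3–4 rows of Table 3 (Section 6.6.1) and in Section 12.3.1. A sample with ionized calcium alone therefore complies with the protocol.

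After a Grade 2 reaction, Table 3 allows the infusion to resume "only after patient recovery, with slower infusion rate and with close monitoring". Its footnote a has the remaining dose given the same day if a new infusion must be prepared. After Grade 3 or 4, treatment stops permanently.

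**The concern.** Ionized calcium is a part of total calcium, so a limit on the part should be roughly the limit on the total times the ionized share. The printed pair implies a share of about one sixth. If the true share is well above that, the ionized limit is much the stricter of the two. The same patient could then meet the calcium criterion on one measure and not on the other.

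What is at stake is a dosing hold. With exactly one other TLS marker abnormal, calcium decides whether the two-abnormality rule is met. After a Grade 2 reaction, that separates omitting isatuximab until the chemistry resolves from resuming the infusion the same day.

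**Working it through.** **Inputs.** Corrected limit 7.0 mg/dL (1.75 mmol/L) and ionized limit 1.12 mg/dL (0.3 mmol/L), both from Table 4. Molar mass of calcium 40.078 g/mol. The ionized share *s* is not in either document. I assume 40% to 55%, with 35% to 60% as a wider check, and take it as a share of corrected calcium, which equals measured calcium at albumin 4 g/dL by footnote a.

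**1. Reproduce the printed figures.** mmol/L = mg/dL × 10 / 40.078.
- 7.0 × 10 / 40.078 = 1.747, printed 1.75.
- 1.12 × 10 / 40.078 = 0.279, printed 0.3.

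Both pairs hold to the precision shown. The conversion is not the fault.

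**2. Share at which the two limits coincide.**
- In mg/dL: 1.12 / 7.0 = 16.0%.
- In mmol/L: 0.3 / 1.75 = 17.1%.

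**3. Ionized value matching the corrected limit** (1.75 × *s*).

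| Assumed share | Matching ionized value (mmol/L) | Ratio to 0.3 |
|---|---|---|
| 35% | 0.61 | 2.0 |
| 40% | 0.70 | 2.3 |
| 55% | 0.96 | 3.2 |
| 60% | 1.05 | 3.5 |

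**4. The same gap read the other way.** Total calcium at which the ionized limit would trigger (0.3 / *s*):
- 0.3 / 0.40 = 0.75 mmol/L.
- 0.3 / 0.55 = 0.55 mmol/L.

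An ionized-only sample would leave unflagged any corrected calcium from there up to 1.75 mmol/L.

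**5. When this can change a decision.** All of these must hold:
- the TLS sample reports ionized calcium only;
- the reaction is Grade 2, since Grade 3–4 stops the drug anyway;
- it falls within 7 days of the start of treatment, because Table 4 counts nothing later;
- exactly one other TLS marker is abnormal, since with none the rule fails regardless and with two or more it is met regardless.

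The documents do not say whether the result is back before a same-day resumption, and give no joint frequency. In the global study's 20 mg/kg QW/Q2W arm, 13 of 25 patients (52%) had an infusion-related reaction (protocol Table 1). The Grade 2 share is not given, so I claim no rate.

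**6. Timing.** Amendment 04, dated 14-Dec-2018, already reports results from the first analysis. Section 6.7.2 sets that cutoff 4 months after the last patient's first dose, so the last first dose was no later than about mid-August 2018. Amendment 05 is dated 15-Jul-2020, some 23 months later.

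**The case against.** The strongest reply is that Table 4 never calls the two limits equivalent. Joined by *or*, the ionized limit can only add flags, so a patient with low corrected calcium is caught whatever the ionized result. That stands whenever corrected calcium is measured, but the infusion-reaction sample does not require it.

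There are other safeguards. Section 6.4 requires recovery to baseline or Grade 1 before the next dose. Footnote 15 of Section 1.6 puts corrected calcium and albumin in the chemistry before every Cycle 1 infusion. Tables 3 and 4 are general guidelines, and Table 3 asks for close monitoring. These largely cover later doses. They do not cover a fall in calcium during an infusion that is resumed the same day.

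The size of the gap rests on an assumed share, and the origin of the ionized limit is not stated, so the correct value cannot be settled here. Both points are fair. They limit what can replace the number, but not the direction of the mismatch.

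Five stronger readings are tempting, and the documents do not support them:
- *A conversion error, or swapped units.* Both conversions check. Reading the ionized limit as 1.12 mmol/L would imply a share of 1.12 / 1.75 = 64%, outside the assumed range, so a swap would not make the limits agree either.
- *Independent support from the corrected-calcium range in the Phase 2 SAP (Table 8).* The SAP gives no ionized range. Comparing both limits with its lower bound of 2.2 mmol/L gives [0.3 / (2.2 × *s*)] / (1.75 / 2.2) = 0.3 / (1.75 × *s*). The 2.2 cancels and nothing is added.
- *A separate defect because albumin is missing from the marker list.* Reporting corrected calcium already needs albumin under footnote a.
- *A current hazard to trial patients.* Under Amendment 05 no enrolled patient could still be in the first week. The amendment log lists no change to Table 4, so the limit may have applied during enrolment, but this cannot be confirmed.
- *An effect on the efficacy result.* The calcium limit plays no part in the ORR test. The Phase 2 SAP (Section 2.4.5.6) finds TLS cases by a MedDRA query and describes laboratory signs only among those cases, without naming limits.

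**Conclusion.** The mismatch is real and minor. The printed ionized limit is less than half of the value that would match the corrected limit, on an assumed ionized share of 40% to 55%. The direction needs only a share above about 17%. An ionized-only sample, which the protocol permits at a Grade 2 or higher infusion reaction, would therefore not flag hypocalcemia that the corrected limit flags.

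The practical reach is small. It is confined to Grade 2 reactions within 7 days of starting treatment with exactly one other abnormal TLS marker, and it can no longer change a hold decision for an enrolled patient. ORR, alpha and sample size are unaffected.

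**What to change.** Delete the ionized alternative from Table 4 and keep corrected calcium below 7.0 mg/dL (1.75 mmol/L) as the only calcium criterion. In the infusion-reaction TLS sample, require corrected calcium, meaning total calcium with albumin, in place of the present choice. That phrase occurs in four places: Section 1.6 footnote 9, the Grade 2 and Grade 3–4 rows of Table 3, and Section 12.3.1.

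If an ionized limit is wanted, first check its value and unit against its source. Then state one number consistent with 1.75 mmol/L corrected.

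The cost is one table cell and four identical phrase edits. Albumin can be run on blood already being drawn, and the SAP needs no change. As no enrolled patient is affected, the edit can wait for the next amendment or for any later protocol that reuses the table.

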6.6.3 Guidance in case of hepatitis B reactivation occurring under study treatment

Patient still on treatment at the time of amended protocol 05 will be tested for HBV serology and HBV viral DNA once at any time if HBV status was unknown before treatment started; test will be repeated if clinically indicated.

In case of viral reactivation during study treatment (greater than $1 \log_{10}$ IU/mL increase in HBV DNA or reappearance of HBsAg or detection of HBV DNA in patients with resolved infection) study treatment will be held and specialist consulted for initiation of anti-viral treatment and monitoring of the patient. Resolved infection means previous known history of acute or chronic hepatitis B or the presence of total anti-HBc Ab with/without anti-HBs Ab; HBsAg negative; undetectable serum HBV DNA; and normal ALT levels. Restart of study treatment should be

agreed between the Sponsor, the Investigator and specialist (hepatologist) if infection is controlled. ALT and AST will be closely monitored every month up to study treatment discontinuation. HBV DNA to be done as per specialist advice.

6.7 DURATION OF STUDY PARTICIPATION

6.7.1 Duration of Study Participation for Each Patient

The study duration for an individual patient will include a screening period for inclusion of up to 21 days, the treatment period consisting of 28 day cycles and a follow-up period. Treatment with isatuximab may continue until disease progression, unacceptable adverse event or other reason for discontinuation.

After study treatment discontinuation, an end of treatment (EoT) visit will be done at 30 days to assess safety and ADA, and at 60 days for ADA. If the ADA is positive or the sample is inconclusive at Day 60 then ADA will be repeated every month (± 7 Days) until ADA is negative. Survival status will be collected approximately every 3 months until death or second cutoff date (refer to [Section 6.7.2](#)), whichever comes first.

Patients with PR or better who come off treatment for reasons other than progression of disease will be followed for disease assessment every 4 weeks until progression or initiation of subsequent therapy, the second analysis cutoff date, whichever comes first.

For all patients, any study treatment-related adverse events, and all serious adverse events (regardless of their causal relationship to study treatment) ongoing at the time of study treatment discontinuation will be followed during the follow-up period until resolution or stabilization.

6.7.2 Determination of End of Clinical Trial (all patients)

The first analysis cutoff date for the statistical analysis for ORR will be 4 months after the date of the first dose of the last patient.

Second analysis cutoff date for the updated analysis of ORR and final analysis of time to events data will be 20 months after the date of the first dose of the last patient. Patients still on treatment at time of the second analysis cutoff date and who still continue benefiting from treatment with isatuximab will have the option to continue treatment under this protocol. Study will end after the completion of follow-up for all patients.

